9.7.1 Statistical Hypotheses

This registry is primarily descriptive and designed to detect potential safety signals, rather than test hypotheses. We are specifically interested in detecting whether the prevalence estimates of MCM, preterm birth, and LBW among the live births of pregnant women

exposed to BEXSERO are greater than the prevalence of these outcomes among the general population.

9.7.2 Analysis of Demographics and Baseline Characteristics

Demographic and baseline characteristics will be summarized with simple descriptive statistics and data listings for the evaluable populations of pregnant women and live births. Demographic and baseline characteristics will also be summarized for the population that is lost to follow-up and compared with the evaluable populations to assess potential differences. These data will be reviewed for potential confounding factors that could affect the interpretation of comparisons of registry outcome prevalence estimates with those of comparators. Further details will be provided in the SAP.

9.7.3 Statistical Methods

Overall and stratum-specific point estimates and 95% confidence intervals will be calculated using the binomial distribution for prevalence estimates of MCMs, preterm birth, and LBW among pregnant women exposed to BEXSERO and their live births. For each prevalence estimate, both 1-sided and 2-sided 95% confidence intervals will be calculated and reported. One-sided confidence intervals are appropriate as we are specifically interested in detecting outcome prevalence estimates greater than their respective reference prevalence, and 2-sided confidence intervals will provide further description of the accuracy of the estimates.

Because most structural defects have their origins in the first trimester of pregnancy during the period of organogenesis, analyses of MCM will be stratified by trimester of exposure, if applicable. It is expected that the vast majority (99%) of prenatal exposures will occur during the first trimester before the pregnancy is recognized. The prevalence of combined MCMs reported to the registry will be calculated as a proportion with the number of MCMs as the numerator and the number of live births as the denominator. Pregnancy losses with reported MCMs occurring at or after 20 weeks' gestation will be included in the numerator of the estimate of risk for MCMs to increase sensitivity and to allow comparison of outcomes with the CDC MACDP, which calculates prevalence by this convention. A secondary analysis will be conducted including pregnancy losses with reported MCMs occurring at less than 20 weeks' gestation. The prevalence of combined MCMs in exposed cases will be compared with that of the CDC MACDP (Correa, 2007).

Only cases meeting the CDC MACDP criteria for a defect or with 2 or more conditional defects will be included in the primary analysis. Single minor defects do not constitute a MCM according to the CDC MACDP classification; therefore, they will be listed in the report, but not included in the primary analysis.

The prevalence of preterm births and LBW will be calculated as proportions, with the number of live births as the denominator. These prevalence estimates in exposed cases will be compared with those of the CDC NVSS (Martin, 2015). Because MCMs are often associated with preterm birth and LBW, sensitivity analyses will be performed excluding infants with MCMs from the numerator and denominator when prevalence estimates are determined for these outcomes.

Formulas for the calculation of prevalence of the primary outcomes are presented below:

$$\begin{aligned} \text{MCM prevalence} &= \frac{\text{Number of live births and fetal losses occurring at } \geq 20 \text{ weeks gestation with MCM}}{\text{Number of live births (all fetal losses excluded from denominator per MACDP convention)}} \\ \text{Preterm birth prevalence} &= \frac{\text{Number of preterm live births}}{\text{Number of live births}} \\ \text{LBW prevalence} &= \frac{\text{Number of LBW live births}}{\text{Number of live births}} \end{aligned}$$

The MCM outcome data will be stratified by the earliest trimester of exposure to BEXSERO[®]. For this registry, gestational weeks are estimated from the most reliable EDD as reported by the HCP. If a CEDD is provided by the HCP, it will be used instead. The date of conception will be calculated as the most reliable EDD minus 38 weeks. If the EDD is not available or never estimated, the first day of the LMP may be used to estimate gestational age. The second trimester will be considered to begin at week 14, and the third trimester, at week 28. If there is a discrepancy between gestational age calculated from the LMP and reported gestational age, the HCP will be asked to verify the data.

If it is feasible, descriptive comparisons between the registry and an appropriate internal and/or external comparison group will be examined (see Section 9.2.3 for a description of potential reference groups).

Methods to Control for Confounding and Effect Modification

For analyses of associations between pregnancy outcomes and BEXSERO exposure, confounding and effect modification will be evaluated descriptively. A detailed description of these analyses will be available in the SAP. Potential confounders/effect modifiers may include the following:

- Maternal characteristics (e.g., age, ethnicity, race)

- Previous pregnancy outcomes (e.g., MCMs, stillbirth)
- Pregnancy complications (e.g., preterm labor, eclampsia, placental abruption)
- Comorbidities (e.g., diabetes, hypertension)
- Concomitant exposures (e.g., medications, alcohol, tobacco)
- Infant/fetus sex

Subgroup Analyses

Analyses will be stratified by trimester of exposure and other subgroups of interest, potentially including number of doses of BEXSERO received, gestational age at enrollment and maternal age. Additional details on subgroup analyses will be described in the SAP. Comparisons may be made to external cohorts, if appropriate.

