
structural or chromosomal defect or combination of 2 or more conditional defects in live-born infants, stillbirths, or fetal losses of any gestational age (including outcomes prior to 20 weeks' gestation or weighing <500 g). This definition is consistent with, but not restricted to, the CDC MACDP definition (which includes conditional defects only if they occur in the presence of a major defect) and thus increases the sensitivity of monitoring.
 
Preterm birth: An infant born at gestational age <37 weeks.
 
Low birth weight (LBW): An infant whose birth weight is <2500 g.
 
Outcome variables will be provided by the obstetric HCP and/or pediatrician attending the birth. The HCP will be asked to describe any congenital malformations observed in the infant or fetus and will also be asked to report the gestational age and birth weight. These 2 variables will be used to calculate preterm birth (gestational age <37 weeks at birth) and LBW (birth weight <2500 g).
 
A teratologist/geneticist will review all reported congenital anomalies and classify them using the CDC's MACDP system. Additionally, the teratologist/geneticist will provide an opinion regarding the possible temporal association of the BEXSERO exposure to the development of observed defects. The SAC will meet periodically to review the data and reach consensus on the coding and classification of MCMs and other outcomes of interest.
 
Other Variables
 
Maternal characteristics: Age, ethnicity, race
 
Prenatal data: LMP, estimated date of delivery (EDD), corrected estimated date of delivery (CEDD)
 
Obstetrical history: Previous pregnancies, live births, stillbirths, SABs, induced abortions (IABs), births with congenital malformations, family history of congenital malformations.
 
Concurrent medical conditions
		

Name of MAH: GlaxoSmithKline Biologicals S.A.	Protocol number: V72_82OB	Date of Protocol Abstract: 12 AUG 16

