
intervals are appropriate, as we are specifically interested in detecting outcome prevalence estimates greater than the respective reference prevalences, and 2-sided confidence intervals will provide further description of the accuracy of the estimates.
 
For MCM, the overall prevalence of MCM will be reported. Since most structural defects have their origins in the first trimester of pregnancy during the period of organogenesis, analyses of MCM will be stratified by trimester of exposure if applicable. It is expected that the vast majority (99%) of prenatal exposures will occur during the first trimester before the pregnancy is recognized. The prevalence of combined MCMs reported to the registry will be calculated as a proportion, with the number of MCMs as the numerator and the number of live births as the denominator. Fetal losses with reported MCMs occurring at or after 20 weeks' gestation will be included in the numerator of the estimate of risk for MCMs to increase sensitivity and to allow comparison with the CDC MACDP, which calculates prevalence by this convention. A secondary analysis will be conducted including fetal losses with reported MCMs occurring at less than 20 weeks' gestation in the calculation of prevalence. The prevalence of combined MCMs in exposed subjects will be compared with that of the CDC MACDP (Correa, 2007). The prevalence of preterm births and LBW will be calculated as proportions, with the number of live births as the denominator. These prevalence estimates in exposed subjects will be compared with those of the CDC NVSS (Martin, 2015).
		
Informed Consent and Ethical Approval: As a post-marketing safety reporting activity, this registry qualifies for exemption of US Health Insurance Portability and Accountability Act (HIPAA) authorization. It also qualifies for a waiver of documentation of informed consent (verbal consent) for adult women who self-enroll, and it qualifies for a waiver of informed consent for de-identified data reported to the registry. If a minor requests participation in the registry and all eligibility criteria are met, the registry will obtain assent from the minor and signed written consent from the parent or guardian. The protocol and informed consent waivers will be submitted to an institutional review board (IRB) for approval prior to registry implementation.		

Name of MAH: GlaxoSmithKline Biologicals S.A.	Protocol number: V72_82OB	Date of Protocol Abstract: 12 AUG 16

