9.3.2 Outcome(s) of Interest

Major Congenital Malformation (MCM): The registry defines, classifies, and codes MCMs with criteria specified by CDC MACDP ([CDC, 2007](#)). Newborn and infant conditions that are not necessarily considered MCMs appear in the Exclusion List for the MACDP. These conditions may be included under certain circumstances by CDC criteria and will be considered “conditional defects” in the registry (e.g., skin tags, webbed toes, etc.). Please see the following link for a listing of all MACDP MCMs and conditions on the Exclusion List:

<http://www.cdc.gov/ncbddd/birthdefects/documents/macdpcode0807.pdf>.

The registry defines an MCM as any major structural or chromosomal defect or combination of 2 or more conditional defects in live-born infants, stillbirths, or fetal losses of any gestational age (including outcomes prior to 20 weeks' gestation or birth weight <500 g). This definition is consistent with, but not restricted to, the CDC MACDP definition. Clusters of conditional abnormalities (as defined by CDC MACDP) and data from aborted fetuses of less than 20 weeks' gestation, when available, will be included to increase sensitivity of monitoring. The MACDP includes conditional defects only if in the presence of a major defect. This registry will consider reports of 2 or more conditional defects as a defect case, to increase signal sensitivity and to capture instances where a combination of conditional events might constitute a major defect or syndrome.

The registry conforms to the CDC MACDP guidelines in disqualifying as defects those findings that are present in infants born at less than 36 weeks of gestation, and are attributable to prematurity itself, such as patent ductus arteriosus, patent foramen ovale, or inguinal hernias. The CDC MACDP classification does include chromosomal defects. Though vaccine exposure is not likely to contribute to a risk for chromosomal defects, the registry includes these defects to maintain this consistency with the CDC MACDP.

Live-born infants with only transient or infectious conditions or with biochemical abnormalities will be classified as being without reported MCMs unless there is a possibility that the condition reflects an unrecognized MCM. Detected and reported transient or infectious conditions or biochemical abnormalities in infants without reported MCMs and defects that are excluded by the CDC guidelines will be noted in an appendix in the registry reports.

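### The primary MCM prevalence uses a wider case definition than MACDP, is compared with MACDP all the same, and has no MACDP-definition figure planned beside it

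*Combined protocol and SAP*

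**What the plan says.** **Registry case definition.** Section 9.7.3 defines what enters the primary MCM analysis: "Only cases meeting the CDC MACDP criteria for a defect or with 2 or more conditional defects will be included in the primary analysis". Section 9.3.2 gives the reason: "This registry will consider reports of 2 or more conditional defects as a defect case, to increase signal sensitivity".

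**Comparator case definition.** Section 9.3.2 states: "The MACDP includes conditional defects only if in the presence of a major defect". The abstract describes the MACDP definition in the same way: "which includes conditional defects only if they occur in the presence of a major defect".

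**The comparison.** Section 9.7.3: "The prevalence of combined MCMs in exposed cases will be compared with that of the CDC MACDP". The abstract has the same sentence for exposed subjects: "The prevalence of combined MCMs in exposed subjects will be compared with that of the CDC MACDP". Section 9.5 takes 2.54% from MACDP as the reference and describes detection as the 1-sided 95% interval lying above the reference.

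**What is matched to MACDP.** Section 9.7.3 puts losses with an MCM at or after 20 weeks in the numerator, in part "to allow comparison of outcomes with the CDC MACDP, which calculates prevalence by this convention". Section 9.7.4 matches the denominator (live births only) and sets out the general principle that the comparator's methods should shape the analysis.

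**Other MCM analyses planned.** These are the addition of losses before 20 weeks (9.7.3), the data with and without pregnancies enrolled after a prenatal test (9.7.4), strata by trimester and other subgroups (9.7.3), and, if possible, enrolment method (9.9).

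**The concern.** A case with two or more conditional defects and no major defect counts in the registry's primary prevalence but not in the figure it is set against. The plan aligns the handling of losses and the denominator with MACDP, but not the case definition. None of the other MCM analyses restricts the numerator to cases that MACDP would count, and the one that adds losses before 20 weeks widens it further.

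The registry exists to see whether prevalence exceeds the general population's (9.7.1), and the 1-sided limit is the tool for that. With few expected cases, a single conditional-only case can move the limit across the reference. A reader of the report would then see an apparent excess over MACDP and could not tell from the comparison whether it rests on cases the comparator leaves out. For the prenatal-test bias the plan looks at the data with and without the affected cases; it has no such check here.

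**Working it through.** **1. Is a MACDP-definition prevalence planned anywhere?** None of the analyses in 9.7 to 9.7.4 and 9.9 supplies one. The protocol defers detail to an SAP on summary statistics (9.7), baseline characteristics (9.7.2), confounding and subgroups (9.7.3) and loss to follow-up (9.7.4). None of these deferrals mentions the case definition. The appendix listing in 9.3.2 covers conditions "in infants without reported MCMs and defects that are excluded by the CDC guidelines will be noted in an appendix in the registry reports"; it is a listing and not a prevalence.

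**2. Inputs.** Reference p0 = 2.54%, 1-sided 5% error, 80% power, binomial distribution, N = 5, 20, 50, 100 and 150 live births (all from 9.5). Denote by d the prevalence of conditional-only cases. The documents give no value, so d = 0.1, 0.25 and 0.5 percentage points is an assumption, for illustration only.

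**3. Reproducing Table 9.5-1 (MCM column).** The critical count c is the smallest count with P(X ≥ c | N, p0) ≤ 0.05. Solve P(X ≥ c | N, p1) = 0.80 and report p1/p0.

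| N | c | p1/p0 | Table 9.5-1 |
|---|---|---|---|
| 5 | 2 | 19.30 | 19.30 |
| 20 | 3 | 7.95 | 7.95 |
| 50 | 4 | 4.23 | 4.23 |
| 100 | 6 | 3.07 | 3.07 |
| 150 | 8 | 2.66 | 2.66 |

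The column is arithmetically correct. It takes the registry's prevalence with no vaccine effect to be 2.54%, which under the wider definition requires d = 0 if nothing else differs.

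**4. What one case does.** The exact 1-sided 95% lower limit (Clopper-Pearson) with x cases is the 5% quantile of Beta(x, N − x + 1). Expected cases at 2.54% are 50 × 0.0254 = 1.27, 100 × 0.0254 = 2.54 and 150 × 0.0254 = 3.81.

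| N | One case fewer | Deciding count |
|---|---|---|
| 50 | 3/50: 1.66% | 4/50: 2.78% |
| 100 | 5/100: 1.99% | 6/100: 2.64% |
| 150 | 7/150: 2.21% | 8/150: 2.68% |

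Each pair straddles 2.54%.

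**5. Illustration with no vaccine effect.** The chance of at least one conditional-only case is 1 − (1 − d)^N. The chance that the limit excludes 2.54% is P(X ≥ c | N, 0.0254 + d).

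| N | At least one such case, d = 0.1 / 0.25 / 0.5 | Limit excludes 2.54%, d = 0 / 0.1 / 0.25 / 0.5 |
|---|---|---|
| 50 | 4.9 / 11.8 / 22.2% | 3.80 / 4.28 / 5.06 / 6.52% |
| 100 | 9.5 / 22.1 / 39.4% | 4.26 / 4.96 / 6.15 / 8.49% |
| 150 | 13.9 / 31.3 / 52.9% | 3.85 / 4.64 / 6.02 / 8.84% |

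From d = 0.1 to d = 0.5 the rise is 0.5 to 2.7 points at N = 50, 0.7 to 4.2 at N = 100 and 0.8 to 5.0 at N = 150. At N = 5 and N = 20 the chance is at most 0.9% and 2.2%.

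**6. A different reference.** Sections 9.2.3 and 9.9 allow age-adjusted and more current references. At an illustrative 2.7% the deciding counts are 4/50, 7/100 (limit 3.33%, against 2.64% with 6) and 9/150 (3.17%, against 2.68% with 8). One case still decides, in two of the three sizes at a different count. The chance of excluding 2.7% goes from 4.6% to 5.1-7.6% (N = 50), from 1.9% to 2.3-4.2% (N = 100) and from 2.1% to 2.6-5.3% (N = 150).

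**The case against.** **Deliberate and disclosed.** The protocol explains the departure and why it wants it. That stands, and nothing here argues for dropping the definition. It justifies the numerator for signal review; it does not make the comparison with MACDP a matched one.

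**Descriptive, with no automatic decision.** Section 9.7.1 disclaims hypothesis testing, and under 9.4.5 action depends on the specifics of the cases. That is fair, and the probabilities above should not be read as error rates of a formal test. Even so, 9.5 and 9.7.3 read the 1-sided interval against the reference.

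**Case review.** Every anomaly is classified by the MACDP system (9.4.2), and the SAC reviews MCM classification before each report (9.4.4). With deciding counts of 4, 6 and 8, conditional-only cases would be seen. Section 9.3.2 also notes that CDC criteria admit some excluded conditions in certain circumstances, so the surplus over MACDP may be smaller than the bare definition suggests. This softens the problem inside the registry. The plan still does not commit to showing the split in the reported comparison.

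**The size is assumed.** This is correct. At d = 0.1 the chance stays at or below 5.0% at every N with the 2.54% reference, and at 2.7% it never reaches 5% for N = 100. One case decides in any exact interval with small counts; what is particular here is that the deciding case may be one the comparator does not count.

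**Other mismatches remain.** Enrolment after a normal prenatal test (9.7.4) may lower the registry figure. So may reporting by the attending provider where MACDP searches actively (9.4, 9.2.3). A matched case definition therefore does not make the two sources fully comparable, and the wording of the fix should say no more than it achieves.

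**Conclusion.** The concern holds. The primary MCM prevalence rests on a wider case definition than the figure it is compared with, and no prevalence on the comparator's definition is planned in the text supplied. This element alone can only raise the registry figure relative to MACDP. The size is not derivable from the documents, and the net bias is unknown because opposing features are left out of the calculation. Under the assumed 0.1 to 0.5 points and the 2.54% reference, the chance of an apparent excess with no vaccine effect rises by 0.5 to 5.0 points across 50 to 150 live births; at 5 or 20 it is negligible. Table 9.5-1 needs no correction on this account. The sponsor should make the change: the report would be usable without it, but its main MCM comparison would not be matched on case definition.

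**What to change.** Keep the registry definition as the primary, sensitivity-oriented figure. In 9.7.3 and the matching abstract text, add:

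> MCM prevalence will also be calculated from cases meeting the MACDP definition only, with the same 1-sided and 2-sided 95% confidence intervals, and this figure will serve as the comparison with MACDP that is like-for-like in case definition. The number of cases with 2 or more conditional defects and no major defect will be stated, and the registry-definition prevalence will be footnoted as broader than the MACDP definition.

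The secondary analysis of losses before 20 weeks stays as it is.

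The cost is one table row, a case count and a footnote. No new data are needed, since reported anomalies are already classified by the MACDP system (9.4.2). The matched figure may rest on slightly fewer cases; the primary numerator and its sensitivity do not change. Fixing this in advance also avoids choosing the restricted figure after an excess has appeared.
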